At Visit 7, participants will return all used and unused research cigarette packs. No more cigarettes will be given. Participants will be allowed to keep their e-cig and unused e-liquid pods until the next visit. Participants will return their e-cig and cigarette use logs. Urine samples for biomarkers will be taken. Participants will complete all biomeasures and questionnaires outlined in Table 1. Participants will be advised to quit smoking completely and provided with the quitline number and sources of free/low cost nicotine replacement therapy (NRT) (see Cigarette Smoking Cessation Tools handout document). The Surgeon General booklet will also be given (see the Consumer Surgeon General Report Booklet document). Participants will be asked about their plans to either (a) go back to their own cigarettes only (b) go back to own cigarettes but supplement with an e-cig, (c) continue using an e-cig only, or (d) quit tobacco/e-cigs completely. Participants will be compensated for completing the study visit and procedures.

A study pulmonologist was added to the study team. We will be monitoring lung function using pulmonary function testing that will be completed at Visits 4-7. Any significant worsening (10% worsening or greater) in pulmonary function will be documented as an adverse event. These adverse events will be reviewed by the Safety Monitors in a timely manner. In cases where the Safety Monitor suspects that a participant may be having a respiratory adverse event related to

the study product, a study pulmonologist will be consulted. The pulmonologist will make any needed medical recommendations and a determination regarding whether the participant is able to continue with the study. For more urgent and/or serious adverse events, the Safety Monitor and/or the study pulmonologist will be consulted and immediate medical attention will be sought if needed.

Procedures during COVID-19:

Visits 3-5 and 7 will be completed in-person. Participants will be screened for COVID-related symptoms using a modified version of the Patient Screening Questions from the Penn State Health website. Remote Visit 6 will be completed remotely over Zoom or the telephone. Questionnaires for visits outlined in Revised Table 1 will be sent to the participant via a survey link before the in-person visit. Participants will be encouraged to complete the questionnaires 2 hours before the visit, but will have up to 24 hours to complete them after the visit. Participants will return their e-cig and cigarette use log. Biomeasures will be taken as outlined in Revised Table 1. No biomeasures will be collected at Remote Visit 6. Women of child bearing potential will be retested for pregnancy at Visits 5 and 7.

The study staff will give participants e-cig and cigarette use logs and instruct them to record daily use at each visit. All participants will be asked about their use of other nicotine/tobacco products and if they vaped/smoked any other substances other than nicotine/tobacco at each visit as this could affect the urine biomarkers collected during the study (e.g. carbon monoxide and cotinine levels). Participants will be encouraged/provided advice to substitute some of their cigarettes with their e-cigarette.

Participants will receive a 4-week supply of research cigarettes (130% of daily consumption) and e-liquid pods to last approximately 28 days until the next appointment. At Visit 5, participants will receive an 8-week supply of e-cigarettes and cigarettes due to Remote Visit 6 being a remote visit. Participants will be asked to return all opened, unopened and empty cigarette packs and all used/unused e-liquid pods to the study center at each visit in order to monitor use.

At Visit 7, participants will return all used and unused research cigarette packs. No more cigarettes will be given. Participants will be allowed to keep their e-cig and unused e-liquid pods until the next visit. Participants will return their e-cig and cigarette use logs. Urine samples for biomarkers will be taken. Participants will complete all biomeasures and questionnaires outlined in Revised Table 1. Participants will be advised to quit smoking completely and provided with the quitline number and sources of free/low cost nicotine replacement therapy (NRT) (see Cigarette Smoking Cessation Tools handout document). The Surgeon General booklet will also be given (see the Consumer Surgeon General Report Booklet document). Participants will be asked about their plans to either (a) go back to their own cigarettes only (b) go back to own cigarettes but supplement with an e-cig, (c) continue using an e-cig only, or (d) quit tobacco/e-cigs completely. Participants will be compensated for completing the study visit and procedures.

A study pulmonologist was added to the study team. We will be monitoring lung function using pulmonary function testing that will be completed at Visits 4, 5, 7. Any significant worsening (10% worsening or greater) in pulmonary function will be documented as an adverse event. These adverse events will be reviewed by the Safety Monitors in a timely manner. In cases where the Safety Monitor suspects that a participant may be having a respiratory adverse event related to the study product, a study pulmonologist will be consulted. The pulmonologist will make any needed medical recommendations and a determination regarding whether the

participant is able to continue with the study. For more urgent and/or serious adverse events, the Safety Monitor and/or the study pulmonologist will be consulted and immediate medical attention will be sought if needed.

Follow-up Visit 8 (Week 20)

All participants will be followed up at a visit 4 weeks after their last visit of the Randomized Phase in order to find out their cigarette/e-cig consumption and any attempts in abstinence after participating in the randomized portion of the trial. Participants will return any final e-cigs and e-liquid pods to the study team by either dropping them off to the researcher or scheduling a pick up time with the researcher. If neither of these options can be arranged the participants will be advised how to properly dispose the products themselves. Participants will complete an exhaled CO measurement plus all measures listed in Table 1. Participants will be compensated for completing the study visit procedures.

Procedures during COVID-19:

Remote Visit 8 will be completed remotely over Zoom or the telephone. All participants will be followed up 4 weeks after their last visit of the Randomized Phase in order to find out their cigarette/e-cig consumption and any attempts in abstinence after participating in the randomized portion of the trial. Questionnaires for visits outlined in Revised Table 1 will be sent to the participant via a survey link before the in-person visit. Participants will be encouraged to complete the questionnaires 2 hours before the visit, but will have up to 24 hours to complete them after the visit. Participants will return their e-cig and any e-liquid pods in a pre-paid envelope addressed to the study site. In cases where participants report being abstinent from cigarettes in the past 7 days at Visit 8, we will verify with a carbon monoxide reading (which biochemically validates abstinence). We will plan to send individual CO monitors for participants that can be mailed to the participant's house. Participants will use the personal devices to complete a CO measurement while on ZOOM with the researcher. Participants will be compensated for completing the study visit procedures.

Unscheduled Visits

If a participant requires additional study product (e.g., cigarette packs, e-cig pods), or if the e-cig fails, they may call the research center to schedule a time to obtain additional products (in-person).

Appointment Reminders

Phone call, text, and email reminders will be used throughout the study to remind participants of their next visits (approximately 1-2 days prior). Also, visit time/date confirmation and study center directions will be emailed/mailed to the participant prior to Visit 1 (see First Appointment Reminder document). For participants who allow us to contact them through phone and text messaging, the study team will be using Google Voice to call or text participant reminders of the study visit and reminders to complete the study surveys with the REDCap survey link. Google Voice is phone service that allows researchers to communicate with participants without revealing their personal phone numbers. The study team will save participants phone number with their study ID. Participants will be told not to share PHI through this phone number.

Biospecimen Processing

All urine samples collected will be stored and analyzed in the project biomarkers core lab led by [name].

Data Collection via Phone

If participants are unable to attend an in-person study visit, the researcher will attempt to collect data over the phone. Participants will not be compensated for data provided through this method.

Missed Visit Procedures

Participants will be called at least once to reschedule a missed Visit 1. For participants who do not show up for any other in-person visit, up to 3 phone/email attempts will be made to contact them to reschedule their appointment.

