3.0 Inclusion and Exclusion Criteria

3.1 Inclusion Criteria

1. Ages of 21–70
2. Smoke ≥ 5 cigarettes per day for at least the prior 12 months
3. Smoke regular, filtered cigarettes or machine rolled cigarettes with a filter
4. Exhaled CO measurement of ≥ 6 parts per million at baseline
5. No serious cigarette smoking quit attempt or use of any FDA-approved smoking cessation medication in the prior 30 days (includes any nicotine replacement, varenicline, bupropion [used specifically as a quitting aid])
6. No plans to quit smoking within the next 3 weeks
7. History of a mental health condition like depression, anxiety, panic attacks, ADHD, schizophrenia, an eating disorder, or any other mental health condition and/or have a past history of receiving treatment, counseling or medication for a mental health condition

8. Must be willing to both switch to a different type of cigarette that may contain a different amount of nicotine and to try an e-cig to substitute for some of their cigarettes
9. Must be willing and able to respond to contacts from study staff or attend visits over the study period (not planning to move, not planning extended vacation, no planned surgeries)
10. Must meet lifetime diagnostic criteria for a current or lifetime unipolar or bipolar mood disorder (e.g. major depressive disorder, major depressive episode, manic episode, hypomanic episode, bipolar disorder), an anxiety disorder (e.g. panic disorder, obsessive-compulsive disorder, post-traumatic stress disorder, agoraphobia, social anxiety disorder, generalized anxiety disorder), a psychotic disorder (e.g. mood disorder or other psychotic disorder), or an eating disorder (e.g. anorexia or bulimia) based on the MINI-International Neuropsychiatric Interview Standard (version 7.0.2).(34)
11. Able to read and write in English
12. Able to understand and give informed consent
13. Access to a computer/smartphone with e-mail and a reliable internet connection

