7.2 Study Procedures

All study visits will occur in a private clinic room in the Penn State Clinical Research Center.

Procedures during COVID-19:

Visits 1, 6, and 8 will be done remotely either over Penn State Health Zoom or over the telephone. Questionnaires will be administered via e-mailed or texted link to REDCap, and completed on the participant's own computer/cell-phone, with their answers securely saved in REDCap. All other study visits will occur in a private clinic room in the Penn State Clinical Research Center.

Once in-person research is allowed again, the study will return to previously approved procedures.

Based on the restrictions set by the Dean (Participant mask removal must PAUSE for all observational studies at the College of Medicine), the study team will no longer perform exhaled CO or PFT tests during visits. With this modification there will be no need for participants to take off their mask during study visits. Once the restrictions are lifted, the study team will go back to collecting these samples during the study visit.

Visit 1 (Week -3)

During Visit 1, participants will be screened in person using Screener 2. They will be asked to provide photo ID to verify the age given in Screener 2. If the participant meets eligibility using Screener 2 they will be asked to provide informed consent. Informed consent will be obtained by research staff. During this process, the usual discussion of procedure, risks, side effects, confidentiality, voluntary participation, and right to refuse participation without prejudice will be explained to the participant. Participants must be capable of understanding the nature of this

study, its potential risks, discomforts and benefits before signing consent. Participants will receive a signed copy of the form.

Once the informed consent is obtained the following information will be collected to determine the final eligibility in accordance with inclusion/exclusion criteria mentioned above:

1. Measure exhaled CO
2. Obtain urine sample for pregnancy determination for women of child-bearing potential (those who have had a period in the past 12 months) and who have not had a hysterectomy
3. Obtain medical and concomitant medication histories
4. NIDA Drug Screener
5. Measure vital signs (blood pressure and heart rate)

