7.4.3 Method for Assigning Subject to Treatment Groups

Eligible participants will be allocated to one of the four conditions using a blocked randomization with a 1:1:1:1 ratio of condition assignments via REDCap. The randomization table will be created by the study statistician and only unblinded staff will have access to it.

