10.0 Risks

Switching cigarette brands: Before being randomized in the study you will switch from your usual brand of cigarettes to study cigarettes that are similar in nicotine to your own brand of cigarettes to smoke for 2 weeks. The cigarettes you are given throughout this study may have different characteristics (i.e. nicotine level, ventilation, length, etc.) than your usual brand. So you could experience symptoms related to different strength or sensory effects from the study cigarettes, such as harshness in your throat or chest.

Increased compensatory smoking: Participants may be given cigarettes that have very low levels of nicotine in them which may lead to compensatory smoking and in turn increased levels of toxicant exposure. In prior studies, compensatory smoking was minimal and higher levels of toxicant exposure were generally not observed. Cigarette consumption and exhaled carbon monoxide will be monitored throughout the trial.

E-cig use: There may be some unknown risks related to the use of e-cigs. The most common side effects associated with using an e-cig are changes in taste, dehydration, mucus in throat/sinus, dry mouth, dry cough, throat irritation, mouth irritation, sore throat, mouth ulcers, dizziness, headache, nausea, and hiccups.

- E-cig liquid contains vegetable glycerin, propylene glycol, and flavorings. It is possible that participants may have an allergy to one of more of these ingredients. Participants with known allergies to these substances will be excluded from the study. The most common reported allergic reaction to these substances is contact dermatitis (or rash).
- There are reports that some people who use e-cigarettes have experienced seizures, with most involving youth or young adult users. Participants with a history of seizures or take medications to prevent seizures will be excluded from the study.

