- There have been some reports of serious lung illnesses among those who used e-cigarettes, and even some cases of death as a result. The cause of all deaths has not been identified. The investigations being conducted by the Centers for Disease Control and Prevention (CDC) and the Food and Drug Administration (FDA) have found that the majority of people experiencing these illnesses were using e-cigarette products that contained tetrahydrocannabinol (THC) and/or products that were bought off the street and not from retail establishments. The e-cigarette products used in this study do not contain THC and were bought from manufacturers where quality testing and control is performed. Nonetheless, participants will be advised to call their doctor immediately if they experience cough, shortness of breath, chest pain, nausea, vomiting, diarrhea, or fever after using their e-cigarette. Participants will be told to only use the e-cigarette and liquid pods (cartridges) given to them by the researchers and to not tamper with their e-cigarette or use other liquids with the e-cigarette device.

Nicotine addiction: Participants may be given an e-cig that contains nicotine, which is an addictive substance.

The amount of nicotine they receive from this product depends on what product they are given and how they use it.

Nicotine withdrawal symptoms: Ceasing nicotine may result in nicotine withdrawal symptoms (e.g., irritability, anxiety, restlessness, depressed mood, increased appetite, fatigue, insomnia/sleep problems, impatience, headache, difficulty concentrating). It is possible that nicotine withdrawal symptoms could affect a pre-existing mental health condition. These symptoms will be monitored at each visit.

New pregnancy or intention to become pregnant: Nicotine, from cigarettes and from e-cigs, is known to be harmful to the developing human fetus. Women who are pregnant or are nursing a child may not participate in this research study. Females capable of becoming pregnant will be administered a pregnancy test prior to beginning the research. Participants must agree to take reasonable and necessary precautions against becoming pregnant during the period of the investigation.

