12.0 Sharing Results with Subjects

This study is not designed to diagnose any disease or condition. However, if during the course of conducting clinical procedures (e.g., blood pressure, pulmonary function test), a participant is found to have a result outside of clinical norms, the result will be discussed with the participant at the visit where the result is identified. This information will be written in the Critical Value Letter so that it can be shared with the participant and/or their doctor. If a woman tests positive for pregnancy, the results will be shared with the participant, they will be withdrawn from the study, and they will be advised to follow up with their doctor for prenatal medical care. Overall study results will not be shared with participants.

A Participant Randomization email will be sent to all participants who were randomized in the study. The email will state their randomization assignments for both the study cigarettes and e-cigarette/pods. They will be told if study cigarettes either contained normal nicotine or very low nicotine and if the e-cigarette pods either contained nicotine or zero nicotine.

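### The eligibility pregnancy test leaves out women who can conceive but have had no period for 12 months, which is narrower than section 10 promises

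*Combined protocol and SAP*

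**What the plan says.** Section 7.2, Visit 1 (Week -3), lists a urine pregnancy test among the eligibility procedures and limits it to "women of child-bearing potential (those who have had a period in the past 12 months) and who have not had a hysterectomy". The COVID-19 text for Visit 2, where eligibility testing moves when Visit 1 is remote, repeats the limit word for word. The parenthesis is the only definition of child-bearing potential in the document.

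Section 10.0 is broader: "Females capable of becoming pregnant will be administered a pregnancy test prior to beginning the research".

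Further tests are planned at Visits 3, 5 and 7 (section 7.2 and Table 1). The text for those visits names women of child-bearing potential but does not repeat the 12-month limit, replace it, or refer back to it.

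Under section 12.0, a woman who tests positive is told, and "they will be withdrawn from the study, and they will be advised to follow up with their doctor for prenatal medical care". Section 3.2 (item 1) excludes women who are pregnant, nursing or seeking to conceive. Section 3.3.1 withdraws a participant who reports a new pregnancy.

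**The concern.** Twelve months without a period is a reasonable marker of menopause only when nothing else explains it. Hormonal contraception can stop periods in a woman who may still conceive. So can an eating disorder, and eating disorders are among the qualifying lifetime diagnoses in section 3.1 (item 10). The age range of 21 to 70 admits premenopausal women, and nothing in section 3.2 removes those whose periods have stopped for such a reason.

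The test is the only objective check on the pregnancy exclusion that the document specifies. Without it, exclusion and advice to seek prenatal care depend on the woman reporting a pregnancy herself. A woman who already has no periods lacks the usual prompt, a missed one, so self-report is weakest in the group left untested. Section 10.0 itself states that nicotine from cigarettes and from e-cigs harms the fetus.

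The stake is therefore mainly a lost opportunity to exclude and advise her, with possible e-cig exposure during pregnancy if the gap persists after randomization.

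**Working it through.** The plan gives no figure to reproduce. The check is a comparison of the rules, followed by a count of tests and weeks under each reading of the later visits.

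**Who each rule covers**

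| Woman | Section 7.2 eligibility rule | Section 10.0 commitment |
|---|---|---|
| Period within 12 months, no hysterectomy | Tested | Tested if capable of pregnancy |
| Had periods until a recent conception | Tested | Tested |
| Hysterectomy | Not tested | Not required |
| Postmenopausal, 12 months or more without a period | Not tested | Not required |
| Premenopausal with a uterus, 12 months or more without a period for another reason, still able to conceive | **Not tested** | **Test required** |

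The rules disagree only in the last row. A gap of less than 12 months does not trigger the problem.

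**Inputs for the count**

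- Scheduled tests: Visit 1 (Visit 2 under COVID-19 procedures), then Visits 3, 5 and 7, giving 4 (section 7.2, Table 1 and Revised Table 1).
- Timing: Visit 1 is week -3, Visit 2 is week -2, Visit 3 is week 0 and Visit 7 is week 16.
- E-cigs are first dispensed at Visit 3 and used through Visit 7 (section 7.4.2).
- Allocation is by "a blocked randomization with a 1:1:1:1 ratio of condition assignments" (section 7.4.3). Arms 1 and 3 receive the 5% e-cig, and 240 participants are to be randomized.

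**Reading A: the 12-month limit applies to the eligibility test only**

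- Tests missed: 1 of 4.
- Delay to her first test: 0 − (−3) = 3 weeks, or 0 − (−2) = 2 weeks under COVID-19 procedures.
- E-cig exposure before that test: none.
- Added nicotine before that test: little or none. Inclusion requires "Smoke ≥ 5 cigarettes per day for at least the prior 12 months" and "No plans to quit smoking within the next 3 weeks", and the cigarettes handed out at Visit 2 are described in section 10.0 as "study cigarettes that are similar in nicotine to your own brand of cigarettes to smoke for 2 weeks".

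Even here the first test follows two weeks on study cigarettes, later than section 10.0 promises.

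**Reading B: the limit carries forward to Visits 3, 5 and 7**

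- Tests missed: 4 of 4.
- E-cig use with no test: 16 − 0 = 16 weeks.
- Chance of a nicotine e-cig: 2/4 = 50%, that is 120 of the 240 randomized.
- Net change in nicotine: not computable. Participants are advised to replace some cigarettes with the e-cig, and one of the two nicotine e-cig arms (arm 3) smokes 0.2 mg cigarettes.

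The text settles neither reading. Reading B has some support, because the 12-month wording is the only definition given and women are said to be retested at Visits 5 and 7, which suggests the same group.

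The number of women in the last row of the table cannot be derived. The document gives neither the expected number of women nor the frequency of prolonged amenorrhoea, and I have assumed no figure for either.

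**The case against.** The best reply is that section 10.0 is itself protocol text. Staff who know that a woman can conceive already have an instruction to test her, and a short working definition under a general commitment is ordinary drafting. The examples can also be questioned. A woman on hormonal contraception is already taking the precautions that section 10.0 requires, and the medication history taken at screening would normally reveal it. An eating disorder may be long past, since a lifetime diagnosis suffices, and uncontrolled mental illness is excluded (section 3.2, item 5). Adverse-event questions at every visit and repeated medication review give further occasions for disclosure. The screener scripts (section 4.2.4) and the consent form are not among the documents and may ask about pregnancy.

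Much of this stands as a limit on size. Few women are likely to be affected, many of them are at low risk of pregnancy, and the 16-week scenario is only one possible reading. It does not remove the gap. The eligibility list gives an explicit criterion, and staff who follow it will not test the woman section 10.0 says should be tested. Self-report and medication review do not replace a test, and a stable or past disorder, or contraception that has stopped periods, does not bar entry.

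**Conclusion.** The concern holds. As written, the eligibility rule omits a premenopausal woman with a uterus and 12 or more months of non-menopausal amenorrhoea who can still conceive, and nothing elsewhere in the document corrects it. The point is minor. It concerns participant safety and consistency of wording for a probably small group, and does not touch sample size, power, endpoints or analysis.

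On the narrower reading the consequence is one missed test and a delay of 2 to 3 weeks, with no e-cig exposure. On the wider reading no test is done during 16 weeks of e-cig use. The conclusion rests on taking the parenthesis in section 7.2 as the operative definition, and on the unseen screener and consent material not supplying a broader testing rule.

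**What to change.** In section 7.2, under Visit 1 and under the COVID-19 procedures for Visit 2, replace the parenthesis with a rule that tests all women except those who have had a hysterectomy or are postmenopausal, meaning 12 months without a period and no other medical cause. Add that staff should test when in doubt. State once that this definition applies at every pregnancy-test visit: Visit 1 (Visit 2 under COVID-19 procedures) and Visits 3, 5 and 7.

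The cost is a wording amendment and a few extra urine pregnancy tests at visits where testing already takes place. The medical and medication histories needed to apply the rule are already taken at screening, and Table 1 already schedules urine collection for biomarkers at Visits 3, 5 and 7.
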